*** Identify the subgroups and provide a justification:**

Children less than 18 years of age as only adults are seen at this institution

8. Describe the power analysis used and cite your method of statistical analysis.

If a power analysis is not possible, thoroughly justify the sample size required for the study, including appropriate literature citation (alternatively provide page reference in attached protocol):

Approximately 100 ECMO cases are seen per year in the UPMC Presbyterian

Hospital, of which, approximately 50% require VA-ECMO. We expect to enroll 50-60% of those patients per year. Regarding Specific Aim 1: Feasibility will be defined by a minimum of 80% of patients who will have followed the algorithm on greater than or equal to 90% of the days on ECMO. The data obtained from this pilot and feasibility study will help to establish event rates, transfusion rates and volumes, to inform subsequent larger clinical trials. Incidence of protocol compliance will be analyzed by Chi Square test or Fisher exact test. P value less than 0.05 will be considered significant. Transfusion rates and volumes as well as clinical outcome rates will be analyzed by independent-sample t test or Mann Whitney U test wherever appropriate.

Cognitively Impaired Adults

1. * Provide a justification for the inclusion of adult subjects who are unable to provide direct consent for study participation:

A large proportion of patients will undergo ECMO in an emergent setting, in which they themselves are unable to provide consent due to their clinical status. Once it is determined by an investigator that the patient is unable to provide consent, consent will be obtained from the patient's proxy.

2. * Specify the criteria used to determine that a given potential adult subject is not able to provide direct consent for participation and identify who will responsible for that determination:

If a patient is heavily sedated, unconscious or intubated they will not be able to provide consent and a investigator will make the determination to approach the Proxy for consent.

Research Activities

1. *** Provide a detailed description of all research activities (including screening and follow-up procedures) that will be performed for the purpose of this research study. This description of activities should be complete and of sufficient detail to permit an assessment of associated risks.**

Once the patient is placed on ECMO, baseline arterial blood gas (ABG), complete blood count (CBC), fibrinogen, platelet count, aPTT, PT and TEG will be performed. Simultaneous heparinase and kaolin TEG must be performed any time a TEG is performed. Pertinent TEG results will include: heparinase-kaolin TEG maximum amplitude (MA) in millimeters (mm), heparinase-kaolin TEG r-time in seconds, heparinase-kaolin TEG alpha angle in degrees, and TEG functional fibrinogen (FLEV) MA in mm. These tests will be performed by a perfusionist in the operating room under the oversight of a co-investigator or principal investigator.

For all patients, the above tests will be performed per the algorithm described in Flowcharts 1 and 2 (attached). Flowchart 1 describes transfusion algorithm for patients in the operating room with inadequate hemostasis, >4 cc/kg/hour. Flowchart 2 describes transfusion management in the ICU when bleeding is less than <4 cc/kg/hour.

Once patient has a normal TEG result with adequate hemostasis, either heparin or bivalirudin will be used as the anticoagulant. Transfusion parameters as described above will only be used on patients who are received no anticoagulation or heparin anticoagulation. If patients are receiving bivalirudin as their anticoagulation strategy, the transfusion parameters with TEG application will not apply.

Heparin titration will be based on kaolin TEG r-time, MA, alpha angle and anti-Xa. Transfusion parameters will be based on heparinase TEG results, INR, platelet count, fibrinogen, and CBC per study protocol.

CTICU heparin titration nomogram:

antiXa/TEG/ACT Action

≤0.20 units/ml and r-time < 10 minutes

-Increase infusion rate by 2 units/kg/hour

-Repeat STAT anti-Xa/TEG 6 hours after rate change

**If the anti-Xa AND TEG do not agree, contact investigator and defer to anti-Xa nomogram for treatment

0.21-0.24 units/ml and

r-time >10 minutes but ≤15 minutes -Increase infusion rate by 1 units/kg/hour

-Repeat STAT anti-Xa/TEG 6 hours after rate change

**If the anti-Xa AND TEG do not agree, contact investigator and defer to anti-Xa nomogram for treatment

0.25-0.35 units/ml and r-time >15 but less than 25 minutes and angle between 20 and 50

(therapeutic range) -No changes in infusion rate

-Repeat STAT anti-Xa/TEG every 6 hours for two consecutive results

If therapeutic, order STAT anti-Xa/TEG daily

**If the anti-Xa AND TEG do not agree, contact investigator and defer to anti-Xa nomogram for treatment

0.36-0.45 units/ml and r-time >25 minutes and angle <30 -Decrease infusion rate by 1 unit/kg/hour after this hour

-Repeat STAT anti-Xa/TEG 2 hours after rate change

**If the anti-Xa AND TEG do not agree, contact investigator and defer to anti-Xa nomogram for treatment

0.46-0.069 units/ml and r-time >30 minutes and angle < 25 -Hold heparin infusion for 1 hour

-Decrease Infusion rate by 2 units/kg/hour after this hour

-Repeat STAT anti-Xa/TEG 2 hours after rate change

**If the anti-Xa AND TEG do not agree, contact investigator and defer to anti-Xa nomogram for treatment

≥ 0.70 units/ml and no sign of TEG clotting -Hold heparin infusion for 2 hours

-Decrease infusion rate by 6 units/kg/hour after 2 hours

-STAT aPTT/TEG 2 hours after rate change

**If the anti-Xa AND TEG do not agree, contact investigator and defer to anti-Xa nomogram for treatment

TEG anticoagulant parameters based upon:

48. [name]. Personal Communication from [name] from Mayo Clinic from retrospective data analysis. 2014; November.

In addition to using the anti-xa level per the CTICU heparin nomogram as detailed above, TEG will also be used to help manage the anticoagulation, based on kaolin TEG r-time and alpha angle. Goals are set as: TEG r-time between 15 and 20 minutes and TEG alpha angle between 30 and 50 degrees. Heparinase and kaolin TEGs will be drawn each time. The heparinase and kaolin TEGs drawn will be able to show a more complete picture of coagulation, in that the heparin effect will be removed (while a patient is receiving heparin for anticoagulation) and underlying coagulopathy can be treated if found. Further, kaolin TEGs, while patients are receiving heparin, will be used for further anticoagulation management, as discussed above.

NOTE: While the ACT is not used at our institution for guiding anticoagulation therapy, many hospitals use this as the only anticoagulation guide. Thus, it would be appropriate to compare anti-xa as well as TEG to the ACT for the gathering of further data. Each time an anti-xa and TEG is drawn per the protocol, an ACT will also be drawn for study purposes.

Transfusion Parameters:

Hematocrit <22.5% or Hemoglobin <7.5 g/dl transfuse 2 units PRBC and recheck CBC

Platelet Count <100,000/uL or heparinase TEG MA <50 mm transfuse 1 dose of platelets

Signs of bleeding and heparinase TEG r-time >20 mm and an INR > 2.0 with clinical signs of bleeding transfuse 4 units of FFP

Signs of bleeding and Fibrinogen <180 mg/dL and heparinase TEG angle less than 30 mm 1 dose cryoprecipitate (4units = 2.0 grams fibrinogen)

TEG transfusion parameters based upon:

48. [name]. Personal Communication from [name] from Mayo Clinic from retrospective data analysis. 2014; November.

Thromboelastography-Guided Transfusion Algorithm Reduces Transfusions in Complex Cardiac Surgery. Anesth Analg 88, 312-19.

The following parameters will specifically be investigated/recorded:

- Patient characteristics (sex, age, indication for ECMO, VV or AV ECMO, cannulation sites)
- Chest tube output and overall estimated blood loss
- Pre-ECMO/Pre-operative anticoagulation, including heparin, low molecular weight heparin, and other anti-aggregants including cyclooxygenase inhibitors such as aspirin, adenosine diphosphate receptor inhibitors such as clopidogrel, Glycoprotein IIb/IIIa (GPIIb/IIIa) inhibitors, phosphodiesterase inhibitors, adenosine reuptake inhibitors, and thromboxane inhibitors.
- Number of transfusions required while on ECMO (primary outcome)
- Time between transfusions
- Type of products transfused
- Pump exchanges required
- Oxygenator exchanges
- Occurrence of pump circuit clotting and clots in the oxygenator (visible clot which did not require circuit/pump exchange)
- Time to weaning from/removal of ECMO
- Need for surgical intervention for hemorrhage
- Occurrence of clinical thrombotic or hemorrhagic event (stroke for example)
- Specimen turn-around time for standard labs tests (CBC, ACT, PT, PTT, anti-Xa, INR, platelet count) and TEG results

Data will be collected for each enrolled patient until they are discontinued from ECMO.

2. Upload a copy of all materials used to collect data about subjects: (Attach all surveys, interview/focus group scripts, and data collection forms except for case report forms, SCID or KSADS):

Document Category Date Modified Document History

There are no items to display

3. * Will blood samples be obtained for research purposes?

Yes No

*** Provide the volume per withdrawal, total volume and frequency, and qualifications of individual performing the procedure:**

Blood drawn from the patient will come out of a pre-existing arterial line and will include a 1.0 ml syringe every 2-6 hours, depending on the value of the previous TEG and other standard of care tests (arterial blood gas, complete blood count, fibrinogen, platelet count, anti-xa). Patients will have on average 15 TEGs drawn over the course of the trial, for a total of 15ml of blood drawn for this study.

Consent Process

Enter N/A in response to the following questions if a Waiver of Consent is requested for all research activities or if no subjects are being enrolled.

1. * Indicate where the consent process will take place and at what point

consent will be obtained:

The informed consent process will take place in the hospital pre-operative area prior to performing any of the research interventions/interactions.

2. * Describe the steps that will be taken to minimize coercion and undue

influence, including assurance that there is sufficient time for subjects to make an informed decision:

In order to minimize the possibility of coercion or undue influence, the patients will be first informed that the choice of participation in the study is totally voluntarily in nature, and they will receive the standard of care when they decide not to participate in the study. Prospective patients will be encouraged to ask questions and to discuss the study with others during the consent process.

3. For studies that involve multiple visits, describe the process to ensure

ongoing consent:

Not applicable

4. * Steps to be taken to ensure the subjects' understanding:

The physician investigator will have a discussion about the possibility of being a study participant with the patient/proxy several days to several hours prior to the surgery. The risk, benefits and goals of the study will be presented to the patient. On the day of the surgery, prior to any study procedures, if the patient is agreeable to participation in the study, the patient will sign consent to participate in the study.

If the patient is unconscious, the physicians will review medical record for responsiveness and will consult with one another to determine patient is truly not able to provide consent. In this instance, a proxy will be approached to provide consent.

5. * Are you requesting an exception to the IRB policy related to the informed consent process:

Yes No

Since participants with impaired decision-making capacity to consent will be enrolled, address the following questions:

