2. * Describe the relevant prior experience and gaps in current knowledge including preliminary data. Provide for the scientific or scholarly background for, rationale for, and significance of the research based on existing literature and how it will add to existing knowledge:

A study by Shore-Lesserson, et al in 1999 demonstrated that in patients undergoing cardiac surgery, use of a TEG based transfusion algorithm resulted in less transfusions than a more traditional algorithm based on ACT, platelet count, prothrombin time (PT), and PTT. This result was hypothesized to be due to TEG's ability to provide qualitative assessment of factor and platelet function, rather than solely quantitative results (Shore et al). Another recent study by Weber, et al. demonstrated that the use of rotational thromboelastometry (ROTEM) to guide hemostatic component therapies was superior to laboratory coagulation testing in terms of efficacy and cost (Weber et al). It has been shown that use of ROTEM and TEG is associated with less perioperative blood loss without increases in transfusions or mortality (Tanaka et al).

A retrospective analysis of 578 patients requiring veno-venous (VV) or VA-ECMO over the past nine year period at the University of Pittsburgh Medical Center was accomplished. Data included duration of ECMO, blood products transfused, and complications from ECMO. The data collected also detailed the transfusion of total blood products and packed red blood cells for patients on VV and VA ECMO. VA ECMO appears to be associated with the greatest amount of transfusion, especially on the day of initiation. Furthermore, in reviewing the data, it appears that the patients who required VA ECMO had a surgery, generally cardiotomy, prior to institution of VA ECMO. Resultantly, in many cases, the transfusion of blood products is generally associated with the day of the primary surgery. This preliminary

data is very important in that it is a guide for the investigators in the determination of where the greatest impact can be made in terms of reducing blood transfusion in the operative setting. Because of this data, patients s/p surgery (usually cardiotomy) appear to have higher incidence of transfusion and as a result, a protocolized and algorithmic focus is expected to yield a reduction of blood products in this patient population.

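### The analysis section assigns two-group tests and a P<0.05 rule to a single-cohort pilot without naming groups, and plans no confidence interval for the feasibility proportion or the event and transfusion rates

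*Combined protocol and SAP*

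**What the plan says.** Study Design, item 8 holds all of the analysis text.

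- **Feasibility** is defined as a "minimum of 80% of patients who will have followed the algorithm on greater than or equal to 90% of the days on ECMO".
- **Compliance:** "Incidence of protocol compliance will be analyzed by Chi Square test or Fisher exact test". A threshold of P<0.05 follows.
- **Secondary outcomes:** "Transfusion rates and volumes as well as clinical outcome rates will be analyzed by independent-sample t test or Mann Whitney U test wherever appropriate".
- **Purpose:** the data "will help to establish event rates, transfusion rates and volumes, to inform subsequent larger clinical trials".

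Study Design, item 2 describes a prospective pilot at one centre, with no control arm or allocation. Study Aims, item 1 says that one TEG protocol is used for every enrolled patient. Research Activities, item 1 adds a qualification: the TEG-based transfusion parameters are not applied to patients anticoagulated with bivalirudin.

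The size is 50 participants in two years under Basic Study Information, item 3, and 100 under Study Design, item 1.

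**The concern.** Fisher exact, independent-sample t and Mann-Whitney U tests each compare independent groups, and the plan does not say which groups. A chi-square test needs either groups or a null value, and neither is given. An analyst would have to choose the contrast, possibly after seeing the data, with a P<0.05 rule already in place.

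The pilot's product is a set of estimates: a feasibility proportion, event rates, and transfusion rates and volumes for designing a larger trial. Item 8 gives no estimator, denominator or interval for the rates, and no interval for the feasibility proportion. A later trial could be sized on point estimates whose imprecision was never reported.

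**Working it through.** **1. Can a stated figure be reproduced?** No. Item 8 gives no power, effect size or precision target. Only its accrual arithmetic can be checked. It puts ECMO cases at about 100 a year, about half of them VA, and says "We expect to enroll 50-60% of those patients per year".

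- If this refers to VA cases: 100 × 0.50 × 0.50 to 0.60 = 25 to 30 a year, or 50 to 60 in two years.
- If it refers to all ECMO cases: 100 × 0.50 to 0.60 = 50 to 60 a year.

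**2. Does any contrast in the documents fit the tests?**

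| Candidate | Where it appears | Fit |
|---|---|---|
| VV versus VA ECMO | Contrasted in Study Aims, item 2; VA share in Study Design, item 8; type recorded in Research Activities, item 1 | Independent groups, so the tests could be run; never linked to them |
| Heparin or no anticoagulation versus bivalirudin | Research Activities, item 1 | Same |
| Historical series: "A retrospective analysis of 578 patients requiring veno-venous (VV) or VA-ECMO over the past nine year period" | Study Aims, item 2 | Possible for transfusion, and the text says that "a protocolized and algorithmic focus is expected to yield a reduction of blood products in this patient population"; but it is presented as preliminary data. Not possible for compliance, since those patients had no study algorithm to follow |
| ACT against anti-Xa and TEG: "it would be appropriate to compare anti-xa as well as TEG to the ACT for the gathering of further data" | Research Activities, item 1 | Values drawn together in the same patients, so paired; not compliance, transfusion or event outcomes |
| One-sample chi-square against 80% | Threshold in Study Design, item 8 | Computable, but no such null is stated; does not explain Fisher, t or Mann-Whitney |

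**3. How imprecise are the estimates?** For x patients out of n, the exact (Clopper-Pearson) 95% limits are:

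- lower = 0.025 quantile of Beta(x, n − x + 1)
- upper = 0.975 quantile of Beta(x + 1, n − x)

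N is taken from the documents. The 20% event rate is an assumption for illustration.

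| Quantity | N=50 | N=100 |
|---|---|---|
| Observed 80% feasibility | 40/50: 66.3–90.0% | 80/100: 70.8–87.3% |
| Illustrative 20% event rate | 10/50: 10.0–33.7% | 20/100: 12.7–29.2% |

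Each interval spans about 24 points at N=50 (90.0 − 66.3 = 23.7) and about 17 at N=100 (87.3 − 70.8 = 16.5).

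**4. How often is the 80% rule met by chance?** Binomial probability of at least 40/50 or at least 80/100:

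| True proportion | N=50 | N=100 |
|---|---|---|
| 70% | 7.9% | 1.6% |
| 75% | 26.2% | 14.9% |
| 80% | 58.4% | 55.9% |
| 85% | 88.0% | 93.4% |

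At N=50, a true proportion of 75% passes about one time in four. An interval beside the result would show how close such a pass is.

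**The case against.** The strongest reply is that the plan is under-specified rather than unworkable. VV versus VA is a natural contrast: the background compares their transfusion, item 8 mentions VA in the same paragraph as the tests, and ECMO type is recorded for each patient. The bivalirudin rule supplies a second contrast, and the aim of improving adherence invites comparing adherence across patient groups. This is also a small uncontrolled pilot. Its 80% rule needs no test, and a reader could compute exact intervals for the proportions later from reported counts.

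Much of this stands. A reader might infer that the tests cannot be run at all; the documents do not support that, because within-cohort groups exist. A reader might also infer that the whole cohort is managed alike; the bivalirudin exception says otherwise for transfusion.

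It does not close the gap. None of these contrasts is named for any test, and none would estimate the quantities that the pilot exists to provide. Intervals for transfusion volumes cannot be recovered from event counts.

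**Conclusion.** The point holds in this form: item 8 names two-group tests, a chi-square test without a null, and a significance rule, but no groups. It plans no interval for the feasibility proportion or the rates. The methods therefore do not address the stated aims. It should be fixed before analysis. It does not change the feasibility decision, which can still be made from the observed proportion.

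At the stated sizes, an observed 80% is compatible with 66–90% (N=50) or 71–87% (N=100), and an illustrative 20% event rate with 10–34% or 13–29%.

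A reader might take 25 to 30 patients as the size, which would widen the feasibility interval to 59–93% (20/25) or 61–92% (24/30). No section states that total. It follows only if accrual is read as VA cases and limited to one year, whereas eligibility covers any adult on ECMO and the stated totals are 50 and 100.

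The conclusion rests on the text available. Some pages of the form and both flowcharts are not shown.

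**What to change.** The investigators should first say whether a contrast was intended. Then amend Study Design, item 8:

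1. **Compliance sentence.** Replace it with the proportion of patients meeting the 90%-of-days rule, reported with an exact (Clopper-Pearson) 95% confidence interval beside the 80% criterion. The criterion itself stays unchanged.
2. **Transfusion and outcome sentence.** Replace it with event proportions and exact 95% intervals. Report transfused units and volumes per patient (median and interquartile range, and mean with a 95% interval by a method suited to skewed data) and per ECMO day (total divided by total ECMO days). Give these overall and separately for patients on bivalirudin.
3. **Significance rule.** Remove it unless a specific contrast, such as VV versus VA or the historical series, is named in advance with its groups defined and is labelled exploratory.

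The cost is analysis wording only, with no new patients or data. Borderline feasibility results will look less certain, and P values are given up unless a contrast is named.

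### As printed, the heparin nomogram has no bleeding input, so a patient on heparin who meets the bleeding-triggered FFP or cryoprecipitate parameter is still titrated upward when anti-Xa is 0.24 or lower

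*Combined protocol and SAP*

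**What the plan says.** Unless noted, these statements are in Research Activities, item 1.

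- **Titration inputs.** Heparin is titrated on four quantities: kaolin TEG r-time, MA, alpha angle and anti-Xa. Bleeding is not among them and appears in none of the six nomogram rows.
- **Rows that raise heparin.** Row 1 (anti-Xa up to 0.20, r-time under 10 minutes): "Increase infusion rate by 2 units/kg/hour". Row 2 (anti-Xa 0.21 to 0.24): "r-time >10 minutes but ≤15 minutes -Increase infusion rate by 1 units/kg/hour". Both rows then say "Repeat STAT anti-Xa/TEG 6 hours after rate change".
- **Conflict between tests.** Every row carries the same clause: "If the anti-Xa AND TEG do not agree, contact investigator and defer to anti-Xa nomogram for treatment".
- **Rows that lower heparin.** The two rows just above the therapeutic band say "Repeat STAT anti-Xa/TEG 2 hours after rate change". The top row also retests at 2 hours.
- **Who gets the transfusion parameters.** "Transfusion parameters as described above will only be used on patients who are received no anticoagulation or heparin anticoagulation".
- **FFP trigger.** Signs of bleeding, plus "heparinase TEG r-time >20 mm and an INR > 2.0 with clinical signs of bleeding transfuse 4 units of FFP".
- **Cryoprecipitate trigger.** "Signs of bleeding and Fibrinogen <180 mg/dL and heparinase TEG angle less than 30 mm 1 dose cryoprecipitate".
- **Starting anticoagulation.** Heparin or bivalirudin follows once TEG is normal and hemostasis is adequate.
- **Flowchart 2 (not shown).** Basic Study Information, item 3, places it in the ICU after hemostasis has normalised and heparin has begun. Research Activities describes it as ICU transfusion management for bleeding below 4 cc/kg/hour.
- **Sampling.** Research Activities, item 3, has blood drawn at intervals of 2 to 6 hours, depending on earlier results.

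**The concern.** The two sets of rules can apply to the same patient at the same time, and nothing in the printed text connects them. One gives plasma or cryoprecipitate because the patient is bleeding. The other raises heparin because anti-Xa is low. The adequate-hemostasis condition governs when an anticoagulant is started. It does not say what happens to the rate if bleeding begins later.

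Study Aims, item 1, judges the safety of the TEG protocol on bleeding and thrombotic events. An order that raises heparin during treated bleeding therefore bears on the outcome by which the protocol is assessed, as well as on the patient.

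**Working it through.** The plan gives no figure to reproduce. The check traces the printed rules and then does one short calculation.

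**1. Does the overlap exist?** Yes. The transfusion parameters apply to patients on no anticoagulant or on heparin. Both triggers use heparinase TEG, which the plan adopts so that underlying coagulopathy can be seen and treated while heparin is running.

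**2. What does the nomogram order at low anti-Xa?** I read the anti-Xa nomogram in the conflict clause as the anti-Xa column of the printed table.

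| Anti-Xa (units/mL) | TEG matches row | TEG does not match | Recheck |
|---|---|---|---|
| ≤0.20 | +2 units/kg/hour | call investigator; +2 units/kg/hour | 6 hours |
| 0.21–0.24 | +1 unit/kg/hour | call investigator; +1 unit/kg/hour | 6 hours |

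The TEG result decides whether a call is made. It does not change the rate. At 0.25–0.35 the rate stays the same, and the three higher bands lower it, so the issue is confined to two of the six bands.

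**3. Which route applies to each trigger?** Assume the kaolin r-time is at least as long, and the kaolin angle no larger, than the heparinase value, since heparinase removes the heparin effect.

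- *FFP.* If the threshold means 20 minutes, the kaolin r-time exceeds 20 minutes. Row 1 needs under 10 and row 2 needs above 10 and up to 15, so neither matches and the order comes through the conflict clause.
- *Cryoprecipitate.* Rows 1 and 2 print no angle criterion. A heparinase angle below 30 implies a kaolin angle below 30, which is under the stated 30 to 50 degree goal. Whether that alone counts as disagreement is unclear. The order is the same either way.

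**4. Do the units matter?** R-time appears in seconds (baseline tests), minutes (nomogram and goals) and mm (FFP trigger). Angle appears in degrees except in the cryoprecipitate trigger, where it is in mm. Reading the FFP threshold as 20 minutes, as 10 minutes (an assumed conversion from trace length) or as 20 seconds can change the route and which patients qualify. It does not change the order at anti-Xa 0.24 or lower.

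**5. How much extra heparin?** Extra dose = rate increase × time to recheck.

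- Anti-Xa ≤0.20: 2 × 6 = 12 units/kg. At an assumed 70 kg, 12 × 70 = 840 units (50 to 100 kg: 600 to 1,200).
- Anti-Xa 0.21–0.24: 1 × 6 = 6 units/kg. At 70 kg, 6 × 70 = 420 units (50 to 100 kg: 300 to 600).
- If a sample were drawn and acted on at 2 hours, these fall to 2 × 2 = 4 and 1 × 2 = 2 units/kg.

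**6. Does other visible text close the gap?** No. Data Safety and Monitoring, item 1, sets monthly or quarterly review. Risk and Benefits, item 5, covers unexpected conditions. Neither governs titration.

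**The case against.** The strongest objection is that the finding is an absence, and the likeliest place for the missing rule is not available. Basic Study Information, item 3, ties Flowchart 2 to both heparin and normal hemostasis. This stands as a limit: a reader might infer that the plan has no bleeding rule at all, and the documents support only that the printed text has none.

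Second, the separation is deliberate. Heparinase TEG guides product use, anti-Xa guides heparin, and Risk and Benefits, item 2, puts conventional tests in charge to guard against a misread TEG. That is a sound safeguard and is not disputed here. It answers the question of which test to trust. It does not answer whether to raise heparin during treated bleeding.

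Third, a reader might infer that in the cryoprecipitate case heparin can rise without anyone being called. The text does not establish this, because angle is a named titration input with its own goal, so a low angle may count as disagreement and require the call.

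Fourth, a reader might multiply the 4 cc/kg/hour ICU threshold by 6 hours and present the result as the cost. That would count the whole bleed at its maximum rate and ignore the earlier sampling that the plan permits. It would isolate no part due to heparin. No baseline heparin rate is given either, so the relative size of the increase is unknown.

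Finally, an override tied to the full triggers misses bleeding patients who do not meet them. That is true. A wider pause is a clinical choice for the investigators; the narrow one resolves the conflict that the plan's own rules create.

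**Conclusion.** The concern holds for the printed text. A patient on heparin who meets the full FFP or cryoprecipitate trigger is ordered an increase of 2 units/kg/hour at anti-Xa up to 0.20, or 1 at 0.21 to 0.24, whether or not TEG agrees. The consequence that can be sized is 12 or 6 units/kg of extra heparin by the 6-hour recheck, and less if an earlier draw is acted on.

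This rests on reading the conflict clause as pointing to the printed table, and on Flowchart 2 containing no overriding rule. The documents give no frequency for the combination, which may be uncommon because each trigger needs three conditions at once. No blood loss attributable to heparin can be derived. It should be fixed because the change is small and the present order is the less safe one for a bleeding patient.

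**What to change.** Add one override to the nomogram. While a bleeding-triggered FFP or cryoprecipitate parameter is met:

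- heparin is not increased;
- the investigator is contacted and chooses an unchanged rate or a hold;
- anti-Xa and TEG are repeated at 2 hours, the interval already used after a decrease;
- this takes precedence over the deferral to anti-Xa.

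Anti-Xa priority otherwise stays as it is. If Flowchart 2 already contains such a rule, a cross-reference in the nomogram is enough.

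Correct the trigger units at the same time: angle in degrees, and r-time in minutes throughout. The sponsor should confirm the intended FFP threshold in minutes, since simply relabelling the 20 mm could change which patients qualify.

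The drafting cost is one line plus the unit corrections. The clinical cost is that some bleeding patients will stay below the anti-Xa range for longer. Circuit and oxygenator clotting, which the plan already records, should therefore be reviewed alongside bleeding.

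### The fifth row of the heparin nomogram has an impossible anti-Xa range, and two transfusion triggers carry units that do not fit

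*Combined protocol and SAP*

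**What the plan says.** All the relevant text is in Research Activities, item 1.

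**Heparin nomogram.** There are six rows in rising order of anti-Xa, each pairing an anti-Xa range with a TEG condition. The last three are:

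- Fourth row: "0.36-0.45 units/ml and r-time >25 minutes and angle <30", with the action "Decrease infusion rate by 1 unit/kg/hour after this hour".
- Fifth row: "0.46-0.069 units/ml and r-time >30 minutes and angle < 25", with a one-hour hold and then "Decrease Infusion rate by 2 units/kg/hour after this hour".
- Sixth row: at or above "0.70 units/ml and no sign of TEG clotting", with a two-hour hold and then "Decrease infusion rate by 6 units/kg/hour after 2 hours".

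Each row carries the same tie-break: "If the anti-Xa AND TEG do not agree, contact investigator and defer to anti-Xa nomogram for treatment". The third row, 0.25 to 0.35 units/ml, is labelled as the therapeutic range.

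**Transfusion Parameters.** FFP requires bleeding together with "heparinase TEG r-time >20 mm and an INR > 2.0". Cryoprecipitate requires bleeding, fibrinogen below 180 mg/dL and a heparinase TEG angle below 30, with the 30 given in mm.

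**Declared units.** The list of pertinent TEG results at the start of the item gives MA in millimetres, r-time in seconds and alpha angle in degrees. The nomogram and the anticoagulation goals give r-time in minutes, and the goals give angle in degrees.

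**The concern.** A dosing table should assign every laboratory value to exactly one action, and the fifth row as printed cannot be met. The band it should cover is above the protocol's own therapeutic range, so these are patients whose heparin the table is meant to reduce.

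The protocol's safeguard leads back to the same place. Risk and Benefits, item 2 protects against misread TEG results by letting conventional testing (anti-Xa and ACT) drive management, while Research Activities says that ACT does not guide anticoagulation at this hospital. That leaves anti-Xa as the deciding test, and the printed error is in an anti-Xa bound.

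The two transfusion triggers raise a smaller version of the same problem: a threshold in a unit that does not belong to the quantity measured. The nomogram and triggers are also part of what adherence would be judged against. Study Design, item 8 defines feasibility by the share of patients in whom the algorithm was followed on at least 90% of ECMO days, so the text should say what following it means.

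**Working it through.** **1. Coverage of the anti-Xa scale.** The six ranges come from the nomogram. I checked them on a grid of 0.01 units/ml from 0.00 to 1.00, which has 101 values.

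| Row | Anti-Xa as printed (units/ml) | Grid values covered | Infusion rate change (units/kg/hour) |
|---|---|---|---|
| 1 | up to 0.20 | 21 | +2 |
| 2 | 0.21-0.24 | 4 | +1 |
| 3 | 0.25-0.35 | 11 | 0 |
| 4 | 0.36-0.45 | 10 | -1 |
| 5 | 0.46-0.069 | 0 | -2 after a 1 h hold |
| 6 | 0.70 and above | 31 | -6 after a 2 h hold |

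Covered as printed: 21 + 4 + 11 + 10 + 0 + 31 = 77. Uncovered: 101 - 77 = 24, which are the values 0.46 to 0.69 (69 - 46 + 1 = 24).

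**2. Candidate corrections to row 5.**

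- Endpoints swapped (0.069-0.46): the row covers 0.07 to 0.46, or 40 values. Of these, 39 (0.07 to 0.45) are already in rows 1 to 4, and 23 values (0.47 to 0.69) remain uncovered.
- Upper bound 0.69: the row covers 24 values. The total is 77 + 24 = 101, with no gap and no overlap.
- Any other two-decimal upper bound: below 0.69 leaves a gap before row 6, and 0.70 or more overlaps row 6.

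So 0.69 is the only two-decimal bound consistent with the adjacent rows.

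**3. Whether the TEG half of the row identifies it.** Any result with r-time above 30 minutes and angle below 25 also has r-time above 25 minutes and angle below 30. Every TEG result that meets row 5 therefore also meets row 4's TEG condition, and TEG alone does not separate the two rows.

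**4. Units of the two triggers.**

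| Quantity | List of pertinent results | Nomogram and goals | Transfusion trigger |
|---|---|---|---|
| r-time | seconds | minutes | 20 mm (FFP) |
| angle | degrees | degrees (goals) | 30 mm (cryoprecipitate) |
| MA | mm | not used | 50 mm (platelets) |

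Of the three, mm fits only MA. For angle, both other places that state a unit give degrees, so the number 30 stands and only the unit changes.

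For r-time the other two places disagree with each other. A third possibility is that mm is a distance on the tracing. The time then depends on a chart speed that the documents do not give. As an assumption, 1 to 2 mm per minute would give 20/1 = 20 minutes down to 20/2 = 10 minutes.

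**The case against.** The strongest reply is that these are typing errors whose meaning is plain. Row 5's lower bound of 0.46 and its action are both printed, and the row sits between 0.45 and 0.70, so a clinician holding a result of 0.50 would very probably use it. The tie-break also tells staff to contact the investigator. The nomogram it defers to may be a separate unit document without the error, which the protocol does not settle. Flowcharts 1 and 2, which are said to contain the algorithm, are attachments that are not shown, so whether bedside instructions carry the error is unknown. Study Aims describes the clinicians as experienced with TEG. All of this stands. It lowers the likelihood of harm but leaves the dosing table wrong.

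Three stronger readings are tempting and are not supported.

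- **That patients would be misdosed by a known amount.** A reader might fill the gap from row 4, leaving the infusion 1 unit/kg/hour higher than row 5 intends (-1 - (-2) = +1), or from row 6, leaving it 4 lower (-6 - (-2) = -4). Both require skipping the row that begins at 0.46, and nothing in the documents suggests that anyone would. Row 4 also refers to an hour without printing a hold, so a contrast between holding and not holding is uncertain.
- **That the FFP threshold is wrong by a factor of 60.** This compares 20 minutes (1,200 seconds) with 20 seconds, and the trigger prints neither unit.
- **That 20 minutes is the intended FFP threshold.** The goals expressed in minutes concern kaolin TEG on heparin, whereas the trigger uses heparinase TEG. They may suggest the unit but do not support the value. If the original page prints min and mm is a misreading of it, only the mismatch between seconds and minutes remains.

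**Conclusion.** The fifth heparin row is wrong as written and must be corrected. Its range is empty, and on a literal reading 24 two-decimal anti-Xa values above the therapeutic range have no row. This rests on the printed bounds and on reporting to two decimals, as the other rows do.

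The two unit errors are real but secondary. For cryoprecipitate the numerical threshold is unaffected, and bleeding and low fibrinogen are also required. For FFP the unit is unexplained and the intended value is open, but bleeding and INR above 2.0 are also required.

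The documents do not say how often affected values occur. A reader might infer that the feasibility result is compromised, but no effect on that endpoint is demonstrated, and no sample size, significance level or power figure changes.

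**What to change.** Amend Research Activities, item 1 as follows.

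1. Print the fifth heparin row as 0.46-0.69 units/ml, with clinical confirmation. Check Flowcharts 1 and 2 and any bedside order set for the same error.
2. State the cryoprecipitate trigger as an angle below 30 degrees.
3. Have the sponsor confirm the FFP r-time threshold against the sources it lists for the TEG transfusion parameters, then state it in minutes. Presume no value before that. Change r-time from seconds to minutes in the list of pertinent results so that one unit is used throughout.

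The cost is a text amendment and a re-check of any heparin, FFP or cryoprecipitate decisions already made under these thresholds. No new data or visits are needed.
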